The term postoperative cognitive dysfunction (POCD) describes a deterioration of cognition that is temporally associated with surgery (Lezak MD Neuropsychological Assessment NY 2004). As opposed to delirium, POCD depends on valid assessments of preoperative and postoperative cognitive function. The underlying etiology of POCD remains unclear. Cerebrovascular disease, cerebral hypoperfusion, genetic susceptibility, alteration in neurotransmitter function, neurohumoral stress, and central nervous system (CNS) inflammatory phenomenon have all been suggested, but the principal suspect has been general anesthesia (Silverstein JH et al Anesthesiology March 2007). However, numerous studies suggest that choice of anesthesia is *not* an important factor in the development of POCD (Wu Reg Anesth Pain Med 2004).

There is an absence of guidelines related to orthopedic surgery and cognitive dysfunction risk to inform the decision-making process for proceeding with surgery in the elderly. The largest trial of POCD was published by anesthesiologists and looked at 1,218 patients aged ≥ 60 at baseline, 1 week, and 3 months post operatively, finding an overall incidence of 25.8% for cognitive dysfunction (Moller JT Lancet 1998). Increasing age, duration of anesthesia, little education, a second operation, postoperative infections, and respiratory complications were risk factors for early postoperative cognitive dysfunction (1 week post-op), but only age was a risk factor for late postoperative cognitive dysfunction (3 months post-op). Limitations to this study include the fact that results were not limited to a certain type of surgery (eg.

orthopedics) and a MMSE of ≥ 24 was used to define normal cognition in this population. Currently, the MMSE is seen as an insensitive screening test in which patients with mild dementia may still score within normal limits ≥ 24 (Lezak MD Neuropsychological Assessment NY 2004).

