Since this question of whether POCD is associated with orthopedic surgery has not been extensively investigated in the neurology or orthopaedic literature, we plan to study longitudinal cognitive performance in a cohort of $n=100$ aging patients undergoing elective hip, knee, and shoulder replacement at Regions hospital. Recruitment will take place over a six month period. Consented patients will receive a cognitive battery consisting of standardized measures of attention, learning, memory, processing speed, and mood at baseline and 3 months. In addition to the incidence of post-operative cognitive dysfunction, demographic and clinical variables related to the surgery (eg. age, anaesthesia, medical complications, etc) will be evaluated to identify risk factors. Variables such as cancer, alcohol abuse, and narcotic use are included for evaluation based on the literature suggesting these pre-disposing risk factors may relate to increased risk of POCD. This data will serve to provide valuable information related to risk of cognitive dysfunction following orthopedic surgery, which will not only benefit neurology providers, orthopedic surgeons, but patients who are themselves making informed healthcare decisions, as well.

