In addition, we are interested in the utilization of blood biomarkers as predictive factors of POCD. With central nervous system and peripheral nervous system neuronal injury, the concentration of neurofilament light chain (NfL) has been found to increase in cerebrospinal fluid and blood (Olsson B JAMA Neurol 2018). NfL is a subunit of neurofilaments, which are cylindrical proteins exclusively located in the neuronal cytoplasm, conferring structural stability to neurons. In the setting of inflammatory, neurodegenerative, traumatic, or vascular injury to axons, the release of NfL sharply increases, resulting in detectable levels in the blood and CSF (Disanto G Ann Neurol 2017). A variety of neurological conditions that impact the CNS and cognitive result in elevation of blood and CSF levels of NfL; these include HIV associated dementia, amyotrophic lateral sclerosis, Creutzfeldt-Jakob disease, progressive supranuclear palsy, frontotemporal dementia, Lewy body dementia, and Alzheimer's disease (Gaetani L JNNP 2019). Since NfL is a sensitive, but non-specific marker of axonal injury, it may be an effective tool to distinguish aging patients who are at risk of undergoing pre-operative cognitive decline from those who are experiencing normal aging.

4. Approach

a. Study design

This is a prospective, cohort study evaluating cognition at baseline and post-operatively at 3 months in older adults undergoing orthopedic surgery. Any subjects with a history of cognitive impairment or any abnormal cognitive screening result will be excluded from the study.

Findings from the cognitive testing will be compared between baseline and 3 months, and participants with a 1.5 SD decrease in any cognitive domain will be considered to have developed POCD. We will then determine pre and peri-operative risk factors associated with development of POCD. Finally, serum studies for NfL will be drawn during the baseline visit.

b. Population

We will be enrolling patients presenting to Regions orthopedics and TRIA Woodbury with a scheduled surgery. Patients must have one of the following diagnostic codes:

Diagnostic Code
M16.0 Bilateral primary osteoarthritis of hip
M16.12 Unilateral primary osteoarthritis, Left hip
M16.11 Unilateral primary osteoarthritis, Right hip
M17.0 Bilateral primary osteoarthritis of Knee
M17.12 Unilateral primary osteoarthritis, Right knee
M17.11 Unilateral primary osteoarthritis, Right knee
M19.011 primary osteoarthritis, Right shoulder

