3. *Screening & Baseline Research Visits:* Combined screening and baseline visits will be held at the Neuroscience Center (NSC) or remote, via telephone or video (WebEx). Patients will be consented. A research assistant will review the inclusion and exclusion criteria. Patient demographic factors will be entered into case report forms (CRF) and then into REDCap. The patient will undergo a MOCA evaluation to confirm score ≥ 26 if in person, or > 19 for the MOCA Blind if completed remote. Should patients not meet the study threshold for MOCA, they will be counseled regarding their score and available resources. Patients scoring normally on the MOCA will undergo a cognitive battery performed by NSC research assistant. Patients will undergo a blood draw for NfL at NSC regardless of an in person visit or remote. The blood will be sent to a Boston-based laboratory for processing. Results from cognitive battery and blood draw will be entered into REDCap. Patients who complete screening will receive a \$5 gift card. Patients who complete both the screening and baseline visits will receive a \$10 gift card.
4. *Post-Surgical Clinic Visits:* Patients will return to orthopedic clinic for 3 month post-operative visit. This is not a research visit.
5. *Follow-Up Research Visits:* A follow-up visit will be scheduled at NSC or remote for 3 months post-surgery (+/- 2 weeks). The cognitive battery will be administered. If it is desired by the patient, this visit can be coordinated so that it is paired with the orthopedic follow-up appointment, which is close in location. Results from cognitive battery will be entered into RREDCap. Patients who complete the follow-up research visit will receive a \$10 gift card.

d. Intervention, treatments

A cognitive battery will be performed at baseline and then at 3 months post-operatively. A lab for NfL will be drawn during the screening/baseline visit. This is an observational study. There are no treatment interventions for this study.

e. Outcomes/endpoint and other variable definitions, and instruments used

Presence of POCD as determined by neuropsychometric outcome data at baseline and 3 months will be used as the outcome for all three study aims. The neuropsychological tests indicated have strong test-retest reliability. A reduction of 1.5 SD in any neuropsychological test between baseline and 3 months will indicate presence of POCD.

Cognitive Domain	Subtopic	Neuropsychological Test
Global Cognition		MoCA (versions 1 and 2)

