Attention	Simple	WAIS-IV Digit Span Forward
	Complex/working mem	WAIS-IV Digit Span Backward
	Complex/working mem	Trails B
Learning/Memory	Immediate	HVLT (versions 1 and 4)

	Delayed	HVLT (versions 1 and 4)
	Psychomotor Speed	Trails A
	Psychomotor Speed	WAIS-IV Digit Symbol Coding
Mood	Anxiety	GAD-7
	Depression	GDS-15

f. Statistical analysis plan

The study population will be described by demographics (e.g. sex, age, race, education status) and baseline health (e.g. vision or hearing impairment, medical history). The appropriate summary measures (mean and standard deviation for continuous variables and frequencies for categorical variables) will be reported. Missing data will be assessed and if a large proportion of data is missing (>10%), we will compare baseline characteristics between subjects to determine if this subpopulation is significantly different. Imputation methods will be considered if differences are found. All statistical analyses will be performed in SAS v9.4 and evaluated at the 0.05 significance level, unless otherwise indicated.

Primary Aim: estimate the incidence of post-operative cognitive dysfunction three months after orthopedic surgical intervention.

This will be defined as a 1.5 SD decline from in any one of the cognitive domains tested baseline to three months. The proportion of patients who develop POCD and a 95% confidence interval will be reported.

Secondary Aim 1: determine pre and peri-operative risk factors associated with development of POCD.

We will be primarily interested in the association between incidences of POCD with the following risk factors:

1. History of delirium
2. Presence of post-operative delirium
3. Regional versus general anesthesia
4. >3 sedating medications added during hospitalization
5. History of prior surgery with general anesthesia

We will fit a logistic regression model with presence of POCD as the outcome of interest and the above risk factors as predictors of interest. We will also include age and gender. As an exploratory analysis, we will fit a model with additional risk factors and use score selection to keep variables with the most impact.

Secondary Aim 2: explore the role of serum neurofilament light (NfL) in predicting risk for development of POCD.

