A logistic regression model will be fit with presence of POCD as the outcome of interest and NfL as the predictor of interest to assess the predictive ability of NfL in the development of POCD. We will fit another logistic model that includes NfL and adjusts for the risk factors called out in Secondary Aim 1.

g. Power analysis or statement of precision

In 2018, the orthopaedic center conducted 355 primary knee, 283 primary hip, and 76 primary shoulder/reverse shoulder surgeries. Approximately 450 of these were completed by Drs. [name] and [name], from whose patient populations we will be recruiting. This excludes non-elective cases, revisions, removals, supplements, and unis. The goal of the study is to recruit n=100 subjects. This n was based on both the number of patients we expect to be able to recruit during our timeline, and the estimated study budget. We anticipate the POCD incidence rate will be between 18 and 25% based on previous literature (Moller T et al Lancet 1998). A sample size of 100 produces a two-sided 95% confidence interval with a width equal to 0.157 when the sample proportion is 0.2. This calculation was done using the confidence intervals for one proportion procedure of PASS 2016.

h. Strengths and limitations

Strengths of this study include its focus on post-operative cognitive dysfunction, a topic that is not widely covered in the neurology, orthopedic or anesthesia literature. Furthermore, this study represents a more robust improvement over past investigations of post-operative cognitive dysfunction in normal aging adults in that the Montreal Cognitive Assessment (MOCA) rather than the Mini Mental Status Exam (MMSE) is being used to confirm normal cognition. The MOCA has a 90% sensitivity for mild cognitive impairment whereas the MMSE has an 18% sensitivity for mild cognitive impairment. This will be one of the first studies to evaluate patients exclusively undergoing elective orthopedic surgery whereas prior studies have looked at POCD following a combination of surgical procedures. Finally, this study can be considered pioneering in that it is the first to evaluate the association of blood NfL with risk of post-operative cognitive dysfunction.

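### The POCD case rule counts a mood change as cognitive dysfunction, switches between single tests and domains, and leaves score, SD and direction undefined

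*Combined protocol and SAP*

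**What the plan says.** The case rule appears three times.

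- Section 4.a (Study design): "participants with a 1.5 SD decrease in any cognitive domain will be considered to have developed POCD".
- Section 4.e (Outcomes): "A reduction of 1.5 SD in any neuropsychological test between baseline and 3 months will indicate presence of POCD".
- Section 4.f (Statistical analysis plan, primary aim): "This will be defined as a 1.5 SD decline from in any one of the cognitive domains tested baseline to three months".

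The table in 4.e is the only place that says what the domains and tests are. Its domain column includes Mood, and its test column includes GAD-7 (anxiety) and GDS-15 (depression). Section 3 likewise puts mood inside the battery: "Consented patients will receive a cognitive battery consisting of standardized measures of attention, learning, memory, processing speed, and mood at baseline and 3 months". The same section says that POCD "describes a deterioration of cognition that is temporally associated with surgery".

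POCD so defined "will be used as the outcome for all three study aims". On reliability, 4.e says only this: "The neuropsychological tests indicated have strong test-retest reliability". No coefficient is given.

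**The concern.** There are three faults in one rule.

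1. **Mood.** Read with the table, each of the three wordings lets a 1.5 SD shift on GAD-7 or GDS-15, with cognition stable, make a POCD case. That contradicts the definition in Section 3. The logistic models do not name mood as a covariate, so nothing shows that the scales were meant for another use.
2. **Level.** Section 4.e applies 1.5 SD to single tests; 4.a and 4.f apply it to domains. No section says how tests combine into a domain score. These are different endpoints with different incidences.
3. **Scale and direction.** The plan does not say whether scores are raw or normed, which SD is meant (normative, baseline sample or change score), or which direction is worse on each test. If raw Trails times and raw symptom scores are used, with lower being better, the literal words of 4.a and 4.e would count an improvement.

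At stake is the primary incidence itself. Both logistic analyses are affected too: a predictor related to mood could appear to predict cognitive dysfunction, and two analysts could derive different outcomes from the same text.

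**Working it through.** **The plan's own figure.** Section 4.g says: "A sample size of 100 produces a two-sided 95% confidence interval with a width equal to 0.157 when the sample proportion is 0.2". The simple asymptotic width is 2 × 1.96 × √(0.2 × 0.8 / 100) = 0.1568, which agrees. The half-width is 7.85 points, a yardstick for what follows.

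**Inputs.** From the plan: the 1.5 SD threshold, eight cognitive scores (MoCA, Digit Span Forward and Backward, Trails A and B, HVLT immediate and delayed, Digit Symbol Coding), two mood scores, n = 100, and planning incidence 20%. Assumed, because the plan is silent: no true cognitive decline; threshold in baseline SD units; normal change scores; retest correlation r from 0.6 to 0.9; correlation 0.2 between cognitive changes; a 0.2 SD practice gain on each Trails test; mood changes independent of cognition and of each other.

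**Mood flags.** A change score has SD s = √(2(1 − r)). One mood scale with mean change zero is flagged with probability q = Φ(−1.5/s), and at least one of two with g = 1 − (1 − q)². At r = 0.7, s = 0.775, q = Φ(−1.936) = 0.0264 and g = 5.2%.

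**Cognitive flags.** The chance that at least one of the eight correlated change scores falls by 1.5 SD was simulated. Mood then adds (1 − cognitive rate) × g. At r = 0.7 this is (1 − 0.154) × 5.2 = 4.4 points.

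| r | 0.6 | 0.7 | 0.8 | 0.9 |
|---|---|---|---|---|
| Any of 8 cognitive tests worse, % | 25.5 | 15.4 | 5.5 | 0.3 |
| Either mood scale worse (g), % | 9.1 | 5.2 | 1.8 | 0.1 |
| Points added by mood, mean unchanged | 6.8 | 4.4 | 1.7 | 0.1 |
| Points added if mood worsens 0.5 SD | 18.3 | 15.8 | 10.4 | 2.5 |
| Points added if mood improves 0.5 SD | 1.9 | 0.8 | 0.2 | 0.0 |

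With mood unchanged, mood-only patients are 21–24% of all those flagged; at r = 0.7, 4.4 / (15.4 + 4.4) = 22%. If the two mood changes are correlated 0.6, the additions are 5.9, 3.9, 1.5 and 0.1 points.

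**Against the planning value.** If cognitive-only incidence is 20%, the counted incidence is 20 + 0.80 × g, with g in percent: 27.3, 24.2, 21.4 and 20.1%.

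**Test versus domain.** The eight scores were grouped as MoCA; Digit Span plus Trails B; HVLT; and Trails A plus Coding, with an assumed baseline correlation of 0.4 within domains and a change correlation of 0.2. The cognitive rate is then 11.1, 6.0, 1.8 and 0.1%, and a single mood composite (baseline correlation 0.6) adds 2.4, 1.2, 0.3 and 0.0 points.

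**Which SD.** If the threshold is 1.5 SDs of the change score, each test flags Φ(−1.5) = 6.7% by chance. With independent scores, at least one flag occurs in 1 − 0.9332⁸ = 42% on eight scores and 50% on ten. With correlation 0.5 the figures are 27% and 36%.

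**Literal raw-score reading only.** If a numerical fall on any of the ten rows is a case, including faster Trails times and lower mood scores, the rates with mood unchanged are 40.5, 26.1, 10.4 and 0.7%. With mood improving 0.5 SD they rise to 50.6, 36.5, 18.9 and 3.1%.

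**The case against.** The words used in 4.f and Section 3 make clear that worsening is meant, so few analysts would score a faster Trails time as dysfunction. That is fair: the literal-reading figures show a hazard in the wording, not a likely result, and the conclusion does not rest on them.

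It can also be said that the mood-only figures take direction from intent but membership from the table. That is true, but no consistent reading removes mood without adding something the text lacks. Read literally on raw scores, improved mood makes a case; read as worsening, deteriorated mood does.

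The size objection partly stands. If the claimed strong reliability means r of 0.8 to 0.9, mood adds 1.7 to 0.1 points when unchanged on average, well inside the 7.85-point half-width. At domain level the additions are smaller still. If mood improves by 0.5 SD, the mood-only share of cases falls to about 7% at r = 0.6 (1.9 / 27.4) and lower at higher r. Normality is a rough assumption for short symptom scales, and nothing in the plan supports an average worsening of mood.

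The domain figures depend on grouping. Psychomotor Speed has no domain entry of its own in the table as available here. With Trails A and Coding placed under Learning/Memory, the rates are about 8, 4, 1.2 and 0.04%. Finally, none of the five listed risk factors is a mood variable, so the bias in the logistic models is a possibility whose size is not established.

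**Conclusion.** The concern holds, and the rule must be corrected. That mood is inside the definition, and that 4.e conflicts with 4.a and 4.f on test versus domain, follows from the text and needs no assumption.

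The numerical effect does rest on assumptions. At single-test level with the baseline SD and mood unchanged on average, mood adds between 0.1 points (r = 0.9) and 6.8 points (r = 0.6). Choosing tests or four domains roughly doubles or halves the cognitive rate, or more. The unstated SD matters most: with no true change and all ten scores counted, the chance rate runs from under 1% (baseline SD, r = 0.9) to 50% (change-score SD, independent scores), against an anticipated incidence of 18 to 25%. The stated interval width is arithmetically correct and is not in dispute; the problem is who counts as a case.

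**What to change.** Put one identical rule in 4.a, 4.e and 4.f before the outcome is derived:

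- Define POCD as worsening on the cognitive tests only, and name them.
- For each test, state the score used (raw or normed), the SD that defines the 1.5 SD unit, and the worse direction. If raw Trails times are used, longer is worse; if normed scores with higher meaning better are used, no sign reversal is needed.
- State whether the threshold applies to single tests or to domain scores. If to domains, list the tests in each and how they are combined.
- Take GAD-7 and GDS-15 out of the definition and report their change separately.

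This costs a few sentences in three sections. Data collection is unchanged, and both mood scales are still administered and reported.

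### In-hospital sedating medication enters the Aim 1 model as an unexplained yes/no cut of a count; if risk rises steadily with the count, about a third of the information or more is lost

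*Combined protocol and SAP*

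**What the plan says.** Section 4.f, Secondary Aim 1, names five risk factors of primary interest. The fourth is ">3 sedating medications added during hospitalization". The model follows: "We will fit a logistic regression model with presence of POCD as the outcome of interest and the above risk factors as predictors of interest". Then: "We will also include age and gender". As worded, the fourth factor is an indicator: more than three, or three or fewer.

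The exploratory step does not bring the count back. It says only that "we will fit a model with additional risk factors and use score selection to keep variables with the most impact".

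Secondary Aim 2 reuses the same term: "We will fit another logistic model that includes NfL and adjusts for the risk factors called out in Secondary Aim 1".

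Tests are "evaluated at the 0.05 significance level, unless otherwise indicated". Section 4.g sets the size ("The goal of the study is to recruit n=100 subjects") and the expected incidence ("We anticipate the POCD incidence rate will be between 18 and 25" percent). The documents do not give the distribution of the number of medications, the share of patients expected above 3, or any ground for a change in risk at that point.

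**The concern.** The exposure is a count, but the model sees only which side of 3 a patient falls on. A patient with no added sedating medication is treated like a patient with three, while three and four are treated as different exposures. If risk climbs gradually, that coding discards usable information about one of the five factors the study most wants to assess.

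The loss matters more here because the data are thin. With 18 to 25 expected POCD cases there is little information to spare, and a numeric count would take up the same single model term as the indicator.

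**Working it through.** **Inputs from the documents.** n = 100; incidence 18% to 25%; significance level 0.05 (taken as two-sided); five risk factors plus age and gender.

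**Inputs assumed.** The distribution of the count and the shape of its relation to POCD. The documents give neither, so ranges are shown.

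**The plan's own figure.** Section 4.g gives a 95% interval width of 0.157 at a proportion of 0.2. Check: 2 × 1.96 × √(0.2 × 0.8 / 100) = 0.1568. It reproduces, but it concerns the incidence estimate. No figure is stated for Aim 1.

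**Events per term.** Seven terms if each factor takes one: 18/7 = 2.6 to 25/7 = 3.6. This is the same for the indicator and for a linear count.

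**Information kept if log-odds are linear in the count.** For a single predictor with a modest effect, the efficiency of the indicator relative to the count X is the squared correlation of I(X>3) with X. For a Poisson count with mean m the covariance is m·P(X=3), so

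r² = m · P(X=3)² / [p(1−p)], where p = P(X>3).

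At m = 3: P(X=3) = 0.2240 and p = 0.3528, so r² = 3 × 0.0502 / (0.3528 × 0.6472) = 0.66. On this predictor, 100 patients analysed with the cut inform about as much as 66 analysed with the count.

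| Assumed mean | Share above 3 | Kept | Lost |
|---|---|---|---|
| 1.5 | 7% | 39% | 61% |
| 2 | 14% | 53% | 47% |
| 3 | 35% | 66% | 34% |
| 4 | 57% | 62% | 38% |
| 5 | 73% | 51% | 49% |

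Other assumed shapes:
- Overdispersed counts (negative binomial, size 1, 2 or 5, means 2 to 5) lose 34% to 50%.
- A narrow count of 2, 3, 4, 5 with shares 20/40/30/10% has mean 3.3, variance 0.81 and covariance 1.7 − 3.3 × 0.4 = 0.38. So r² = 0.1444 / (0.81 × 0.24) = 0.74, a loss of 26%.
- If every patient had 3 or 4, nothing would be lost.

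**Power under both shapes.** Simulated one-predictor score tests, n = 100, 20% incidence, Poisson count, 1,500 replicates (simulation error at most √(0.25/1500) = 0.013).

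| Mean | Linear, OR 2.0 per SD: count / cut | Step above 3, OR 4: count / cut |
|---|---|---|
| 2 | 0.79 / 0.62 | 0.42 / 0.63 |
| 3 | 0.78 / 0.61 | 0.59 / 0.77 |
| 4 | 0.80 / 0.54 | 0.46 / 0.66 |
| 5 | 0.80 / 0.39 | 0.26 / 0.48 |

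With a Wald test, the advantage of the cut under a step disappears at mean 5 (0.23 / 0.24).

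**If there is a step, but not at 3.** The same squared correlations, at an assumed Poisson mean of 3, give information kept by the count and by the >3 cut of:
- 42% and 14% for a step above 1
- 62% and 40% for a step above 2
- 56% and 42% for a step above 4

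For the step above 2, the count keeps 3 × 0.2240² / (0.5768 × 0.4232) = 0.62. The cut keeps (0.3528 × 0.4232)² / (0.5768 × 0.4232 × 0.3528 × 0.6472) = 0.40. The order is not universal: at mean 5 a step above 2 gives 33% and 40%.

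**The case against.** The strongest objection is that the better coding depends on a shape nobody has shown. The squared correlation is symmetric: if risk truly steps above 3, the linear count loses exactly what the cut loses under a linear trend, and the power table reverses. A linear count also gives every added drug the same weight, which the documents do not support either. This stands, and it is why the loss must be stated conditionally. It does not justify the plan's choice, because the plan gives no reason to expect a step at 3, and the cut is best only if the step is there.

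A pre-specified cut is also a valid analysis, merely a possibly inefficient one. That stands too.

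A reader might infer several stronger points that the documents do not support:

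- **That the cut leaves residual confounding in the NfL result.** Sections 4.a and 4.c place the NfL draw at the baseline visit, before surgery. Medications added in hospital come later and cannot be a common cause of baseline NfL. Section 4.f also frames Aim 2 as prediction.
- **That one category will be nearly empty.** Under the Poisson assumption this arises at low means (7% above 3 at mean 1.5), but not at means of 2 to 5 (14% to 73%). The true share is unknown.
- **That the powers above are those of the planned model.** They are unadjusted. The planned model has seven terms and 18 to 25 events, and recoding one predictor does not change that limit.
- **That the exact count is already in hand.** Classifying a patient as above 3 needs counting only as far as four, and section 4.c describes no field for this number.

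**Conclusion.** The point holds as a cheap improvement. The plan dichotomises a count at 3 without explanation and names no analysis of the count. If log-odds rise roughly linearly and the count is Poisson-like, the loss is 34% at an assumed mean of 3 and about half or more where few patients fall on one side (61% at mean 1.5, 47% at mean 2, 49% at mean 5).

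These are illustrations under assumptions, not bounds. It would be tempting to report a loss of a third to over half as a fact about this study, but the documents supply neither the spread nor the shape needed to say so. With a narrow count the loss is smaller, and with a true step above 3 the cut generally does better.

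The consequence is confined to one predictor in Secondary Aim 1 and its reuse as an adjustment term in Secondary Aim 2. The primary incidence estimate does not depend on it.

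**What to change.** In section 4.f, Secondary Aim 1, define the factor as the number of sedating medications added during the hospital stay, entered as a single numeric term. Use the same term in the adjusted NfL model so that the two models agree. Report the >3 version as a pre-specified sensitivity analysis, and state the reason for that threshold if there is one. Make sure the case report form captures the exact number rather than only the yes/no classification.

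**Cost.** A line or two in the analysis plan, no extra model term, and one data field if the number is not already recorded. Categories or a spline would add terms that 18 to 25 events cannot readily carry, so they are not suggested.

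**Downside.** The numeric term assumes a roughly linear trend and equal weight per drug. A true step above 3 would be better caught by the cut, which is why it is kept as a sensitivity analysis. The change does not cure the 2.6 to 3.6 events per term.

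### The Secondary Aim 1 model adjusts anaesthesia type and the history factors for post-operative delirium, and for added sedatives of unstated timing, so their coefficients may be attenuated

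*Combined protocol and SAP*

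**What the plan says.** Section 4.f, Secondary Aim 1, opens: "We will be primarily interested in the association between incidences of POCD with the following risk factors". Five factors are then listed. Two concern the patient's past: "History of delirium" (item 1) and, at the end of the list, "History of prior surgery with general anesthesia" (item 5). One belongs to the operation itself: "Regional versus general anesthesia" (item 3). The remaining two are events of the hospital stay: "Presence of post-operative delirium" (item 2) and, listed separately, ">3 sedating medications added during hospitalization" (item 4).

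The analysis is a "logistic regression model with presence of POCD as the outcome of interest and the above risk factors as predictors of interest", with age and gender added, so seven terms in all. The only other Aim 1 model is exploratory: it brings in further candidates and applies score selection. The adjusted model in Secondary Aim 2 carries the same risk factors over, so NfL from the baseline blood draw is also adjusted for post-operative events. Nothing in the document describes a staged model, or says whether a coefficient is to be read before or after adjustment for later events.

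**The concern.** Every factor is named as being of primary interest, so every coefficient will be read as that factor's association with POCD. Yet the coefficients for anaesthesia type and the two history factors hold fixed whether the patient later became delirious and whether more than three sedatives were added. Anything that anaesthesia type or a history of delirium does through those events is taken out of its own coefficient.

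This matters because of how the results are to be used. Section 3 says they should serve "patients who are themselves making informed healthcare decisions", who decide before delirium or in-hospital sedation can be known. Section 9 makes outreach to other departments depend on whether pre-surgical factors turn out to be predictive. Section 3 also calls general anaesthesia the principal suspect while citing work that finds the choice of anaesthesia unimportant. A near-null anaesthesia coefficient could be taken as agreeing with that work when it partly reflects the adjustment.

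**Working it through.** **The plan's own figure.** The only precision figure (Section 4.g) is a 95% interval width of 0.157 at n = 100 and proportion 0.2. Check: 2 × 1.96 × √(0.2 × 0.8 / 100) = 2 × 1.96 × 0.04 = 0.1568. It reproduces, but it concerns the primary aim. No figure is given for Aim 1.

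**Order in time, as far as the text fixes it.**
- Before surgery: history of delirium; prior surgery with general anaesthesia.
- At surgery: regional versus general anaesthesia.
- After anaesthesia, by definition: post-operative delirium.
- Not stated: the added sedatives. They are placed within the hospital stay, but not before, during or after anaesthesia.

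**Illustration.** The documents give no path strengths, so every input below is an assumption except the 20% POCD, which lies in the plan's 18 to 25% range. Assumed: 50% general anaesthesia; under regional anaesthesia, 25% have more than three sedatives and 10% have delirium if not so sedated. History factors, age and gender are left out for simplicity.

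Moderate scenario: general anaesthesia multiplies the odds of sedatives by 3 and of delirium by 2; sedatives multiply the odds of delirium by 2; sedatives multiply the odds of POCD by 3 and delirium by 4; there is no direct anaesthesia effect. An overall POCD of 20% then requires a risk of 0.0965 with neither event, 0.2994 with delirium only, 0.2428 with sedatives only and 0.5618 with both. Weighting by the share of patients in each cell, in that order:
- Regional: 0.675 × 0.0965 + 0.075 × 0.2994 + 0.2045 × 0.2428 + 0.0455 × 0.5618 = 0.163
- General: 0.4091 × 0.0965 + 0.0909 × 0.2994 + 0.3462 × 0.2428 + 0.1538 × 0.5618 = 0.237
- Odds ratio without the two later variables: (0.237/0.763) / (0.163/0.837) = 1.60 from unrounded risks. With them it is 1.00, because no direct effect was assumed.

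The same enumeration for other assumed paths follows. Paths are listed in the order anaesthesia→sedatives, anaesthesia→delirium, sedatives→delirium, sedatives→POCD, delirium→POCD, direct. The last column is the share of about 1,000 simulated trials of n = 100 with p < 0.05 for anaesthesia.

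| Scenario | Assumed odds ratios | OR without later events | OR with them | p < 0.05, without / with |
|---|---|---|---|---|
| No mediation | 1, 1, 1, 3, 4, 2 | 1.89 | 2.00 | 21% / 23% |
| Weak, complete | 1.5, 1.5, 1.5, 2, 2, 1 | 1.11 | 1.00 | 6% / 5% |
| Moderate, complete | 3, 2, 2, 3, 4, 1 | 1.60 | 1.00 | 12% / 5% |
| Strong, complete | 6, 4, 3, 4, 6, 1 | 3.15 | 1.00 | 56% / 4% |
| Moderate, partial | 3, 2, 2, 3, 4, 1.5 | 2.29 | 1.50 | 35% / 11% |

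In the first row the small difference arises because an odds ratio changes when other predictors of the outcome are added; nothing is lost.

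**Events per term**, with 18 to 25 events in 100 patients:
- Five terms (two history factors, anaesthesia type, age, gender): 18/5 = 3.6 to 25/5 = 5.0
- Six terms (sedatives added): 18/6 = 3.0 to 25/6 = 4.2
- Seven terms (delirium added, the same terms as the planned model): 18/7 = 2.6 to 25/7 = 3.6

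**The case against.** The aim is worded as association, in Section 2 and again in Section 4.f, and no causal or total effect is claimed for anaesthesia. Entering all factors together is an ordinary way to look for independent associations. This stands: the planned model is a legitimate analysis and need not be dropped. It does not settle the matter, because the plan does not say which reading applies, and a model that needs post-operative information cannot support advice given before surgery under either reading.

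The odds ratio of 1.00 in three rows of the table is forced by assuming no direct effect. That stands too, so those rows show only the limiting case. Section 4.h says the study cannot assess patients in the first days after surgery, so delirium must come from another source. If it is imperfectly captured, the adjustment would be incomplete and the attenuation hard to predict.

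At n = 100 the practical difference may be small. In the weak and moderate complete-mediation scenarios a non-significant anaesthesia result is likely under either model.

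A reader might also infer that leaving out the joint operated on is a comparable defect. The documents do not support that. Shoulders were 76 of 355 + 283 + 76 = 714 operations in 2018, or 10.6%: about 11 patients in 100, with about 2 events at 20% incidence. Nothing in the documents says how anaesthesia type or POCD risk differs by joint, and the exploratory model is open to additional factors.

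**Conclusion.** The point holds as a structural one. In the planned model, the coefficients for anaesthesia type and history of delirium exclude whatever runs through post-operative delirium and, so far as the sedatives come later, through sedation. They are attenuated if mediation is partial, go to the null if it is complete, and lose nothing if there is none. In the illustrations with mediation, the odds ratio without the later events ranges from 1.11 to 3.15. Those figures rest wholly on assumed paths and are not estimates for this study.

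Two stronger readings are tempting. One is that the plan will erase a real anaesthesia effect; that would need both a real effect and complete mediation, and the documents establish neither. The other is that both adjusting variables follow anaesthesia; the text establishes this for delirium only. Since the aim is secondary and the remedy cheap, this is a worthwhile SAP correction and not a flaw that undermines the study.

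**What to change.** Replace the single reading of the Aim 1 model with steps in time order:

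- **Model A:** history of delirium, prior surgery with general anaesthesia, regional versus general anaesthesia, age and gender. Report the first three from here.
- **Model B:** Model A plus more than three sedating medications. Read only the sedative coefficient here, so that it is not adjusted for delirium, a possible consequence.
- **Model C:** Model B plus post-operative delirium. Read the delirium coefficient here. Model C has the same seven terms as the planned model; keep it as the jointly adjusted, independent-association analysis.

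Label each reported coefficient by what it is adjusted for, and define the sedative variable by its timing relative to anaesthesia. In Secondary Aim 2, make the main adjusted NfL model one that adjusts for pre-operative factors only, say on which side anaesthesia type falls, and add the post-operative events in a secondary model. Do not require a term for the joint; at most, make it a candidate in the exploratory model.

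The cost is SAP wording and two extra Aim 1 fits (A and B) plus one for Aim 2, on variables already planned. The downside is more than one set of coefficients to present. All of them stay imprecise with 18 to 25 events, so the change corrects what is estimated and does not improve power.
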